2.1. Study Rationale

The aim of this dose-ranging study is to determine the safety and immunogenicity of different dose levels of Ad26.RSV.preF in the Ad26/protein preF RSV vaccine to support the refinement of the acceptance criteria for drug product release and stability by generating additional information on clinical safety (for the upper release limit) and immunogenicity (for the lower release limit).

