Study **VAC18193RSV1004** is a multicenter, randomized, double-blind, placebo-controlled Phase 1/2a regimen selection study in 667 participants aged ≥ 60 years in stable health to evaluate the safety and immunogenicity of Ad26.RSV.preF alone, of combinations of Ad26.RSV.preF and RSV preF protein, and of separate administration of Ad26.RSV.preF and RSV preF protein. A significant increase in humoral immune responses including virus neutralization assays (VNAs) and preF antibody titers was observed in the groups combining Ad26.RSV.preF and RSV preF protein compared with Ad26.RSV.preF alone. No relevant differences between the combination groups and Ad26.RSV.preF alone were noted for cellular immune responses measured at the time of primary analysis. All regimens had acceptable safety and reactogenicity profiles, which were similar across groups. Available safety data support that this vaccine is safe and has an acceptable reactogenicity profile.

Study **VAC18193RSV2001** is a multicenter, randomized, double-blind, placebo-controlled Phase 2b proof-of-concept study in approximately 5,800 participants aged ≥ 65 years with and without comorbidities to confirm the potential for efficacy of the Ad26/protein preF RSV vaccine and to assess 3 case definitions of RSV-mediated lower respiratory tract disease.

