4.3. Justification for Dose Level

The dose level of 1×10^{11} vp for Ad26.RSV.preF and 150 µg for RSV preF protein (administered in all 3 cohorts) was selected from the primary analysis of Cohort 2 in study VAC18193RSV1004 and is currently under further evaluation in studies VAC18193RSV1004 and VAC18193RSV2001 (Section 2.2.2).

The lower dose levels for Ad26.RSV.preF in Cohort 1 of the current study were selected based on the assumption that half-log intervals in dose response are biologically meaningful for vaccines.

There are currently no safety data available of Ad26.RSV.preF at a dose level above 1×10^{11} vp. Two higher dose levels of Ad26.RSV.preF (ie, 1.3×10^{11} vp [Cohort 2] and 1.6×10^{11} vp [Cohort 3]) will therefore be assessed in this study. An increase of 0.3×10^{11} vp per dose level could lead to a potential increase of target fill concentration of approximately 15%.

In all cohorts, the dose level of RSV preF protein will be kept constant (150 µg). This dose level has been tested in other (ongoing) clinical studies (Section 2.2.2).

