9.4.2. Immunogenicity Analyses

No formal statistical testing of immunogenicity data is planned. Immunogenicity data will be analyzed descriptively by cohort and group. In addition, for a selection of tables, data may be pooled over cohorts.

Descriptive statistics (eg, geometric mean and 95% confidence interval [CI] for ELISA and VNA data; median and quartiles for ELISpot) will be calculated for continuous immunologic parameters at all timepoints. For the humoral assays, geometric mean fold rises from baseline and corresponding 95% CIs might additionally be calculated. Baseline is considered as the last available assessment before vaccination. Graphical representations of immunologic parameters will be made as applicable.

Frequency tabulations will be calculated for discrete (qualitative) immunologic parameters as applicable.

To explore the dose-response relationship between preF ELISA and different dose levels of the Ad26/protein preF RSV vaccine, a linear regression model will be fitted for each timepoint separately, using data of the active groups of Cohort 1, with the log-transformed preF ELISA titers at the considered timepoint as dependent variable, the number of titration steps as independent variable, and the geometric mean titer (GMT) of preF ELISA of the Ad26/protein preF RSV vaccine (1×10^{11} vp/150 μ g) at the considered timepoint as a fixed intercept.

The linear model $\log_2(\text{preF ELISA}_{\text{timepoint}}) = \text{GMT preF ELISA}_{\text{Ad26/protein preF RSV vaccine } (1 \times 10^{11} \text{ vp/150 } \mu\text{g}), \text{timepoint}} + \text{slope} \times \# \text{titration steps}$ will initially be fitted for the active groups of Cohort 1 but may be extended in a later stage with data of the active groups of Cohorts 2 and 3. A similar model may be fitted as well for other assays.

Depending on the model fit, other models (eg, log-linear models or EMAX models) may be explored as well.

The incidence of neutralizing antibodies to Ad26 might be summarized for participants who are positive for antibodies to Ad26.

Other immunogenicity analyses may be performed to further characterize the immune responses that are generated.

The primary analysis set for the immunogenicity analysis is the PPI set. As a sensitivity analysis, key tables may also be based on the FAS.

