### 5.3.1. Immunogenicity Against RSV

#### 5.3.1.1. Humoral Assays

For humoral assays, N, geometric mean (GMT)§ and corresponding 95% CI of the actual values will be calculated. The fold increases from baseline will be tabulated and graphically presented. *§The mean and corresponding 95%CI will be calculated on the log2-transformed values, and then back-transformed [i.e. 2^mean] and CI [i.e. 2^CI].*

Actual values and fold changes from baseline will be summarized in tables and dot plots, with dots for subject values, and the corresponding geometric mean and 95% CI per time point for each assay. In addition, GMT plots over time, combining the regimens in one graph (without individual subject dots) will also be created.

Ratios of actual values and ratios of fold changes from baseline between humoral assays may also be presented. Subject profiles of the actual values over time will be graphically presented. Reverse distribution curves of the actual values will be provided for selected time points. In the graphs, original values will be displayed on the log2 scale.

A scatterplot of the virus neutralization assay (VNA) versus ELISA will be provided for the most important time points. In these scatterplots the actual values will be shown, even if they are below the LLOQ, but the LLOQ cut-off will be visualized in the graph per assay if some values are below LLOQ.

To explore the dose-response relationship between pre-F ELISA and different dose levels of the study vaccine, a linear regression model will be fitted for each timepoint separately, using data of the active groups of Cohort 1, with the log transformed pre-F ELISA titers at the considered timepoint as dependent variable, the number of titration steps as independent variable, and the GMT of pre-F ELISA of the Ad26/protein pre-F RSV vaccine ( $1 \times 10^{11}$  vp/150 µg) at the considered timepoint as a fixed intercept. The regression slope and 95% one-sided lower confidence limit for the slope will be calculated.

The following linear model will initially be fitted for the active groups of Cohort 1 but may be extended in a later stage with data of the active groups of Cohorts 2 and 3. A similar model may be fitted as well for other assays:

$$\log_2(\text{pre-F ELISA}_{\text{timepoint}}) = \text{GMT pre-F ELISA}_{\text{Ad26/protein } (1 \times 10^{11} \text{ vp}/150 \mu\text{g}), \text{timepoint}} + \text{slope} \cdot \# \text{titration steps} + \text{error}$$

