Depending on the model fit, other models (such as, log-linear models or EMAX models) may be explored as well.

Other exploratory immunogenicity parameters maybe analyzed at the discretion of the sponsor.

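### The only committed model-based dose-response estimate in Cohort 1 is one straight-line slope; no reduced dose is compared with 1x10^11 vp with a confidence interval, so curvature would misstate the first-step loss in either direction.

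*SAP*

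**What the plan says.** Protocol 2.1 says the trial should generate "additional information on clinical safety (for the upper release limit) and immunogenicity (for the lower release limit"). Exploring the humoral dose-response is the primary objective of Cohort 1 (Protocol 3).

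For that objective, SAP 5.3.1.1 specifies a linear regression at each timepoint in the Cohort 1 active groups. Log-transformed preF ELISA is the outcome, with "the number of titration steps as independent variable" and the 1x10^11 vp GMT "at the considered timepoint as a fixed intercept". The output is stated as: "The regression slope and 95% one-sided lower confidence limit for the slope will be calculated".

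Alternatives are left open: "Depending on the model fit, other models (such as, log-linear models or EMAX models) may be explored as well". Protocol 9.4.2 has the same provision. Neither document names a fit statistic, a threshold or a trigger.

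SAP 5.3 and 5.3.1.1 also commit to summaries by cohort, vaccine group and timepoint: N, GMT with 95% CI, fold increases from baseline, dot plots, GMT plots over time and reverse distribution curves. The ratios mentioned in SAP 5.3.1.1 are between humoral assays, not between dose groups.

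**The concern.** To learn what a dose reduction does to the titer, one needs the ratio of the reduced dose to 1x10^11 vp, with its uncertainty. The plan gives this only through the slope, and so only if the log2 titer falls by the same amount at every step.

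The documents give no evidence for that linearity, and there is some reason to doubt it. Every active group also receives 150 µg of protein (Protocol 4.3). Protocol 2.2.2 reports of the earlier regimen-selection study: "A significant increase in humoral immune responses including virus neutralization assays (VNAs) and preF antibody titers was observed in the groups combining" the two components, compared with Ad26.RSV.preF alone. A floor at low Ad26 doses is therefore plausible, and so is a plateau near the top dose. The step spacing rests on the assumption that "half-log intervals in dose response are biologically meaningful for vaccines", which concerns how far apart the doses are, not the shape of the curve.

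At stake is whether a statement about a modest reduction below 1x10^11 vp, read off the slope, would be too optimistic or too pessimistic, with no planned interval estimate to check it against.

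**Working it through.** **Inputs from the documents.** Doses are 1x10^11, 3.3x10^10, 1.1x10^10 and 3.7x10^9 vp (Protocol Table 2), so the step ratios are 3.03, 3.00 and 2.97. SD is 1.3 log2 on Day 15 and 1.1 on Day 183, with 10% exclusions from 50 per arm, leaving 45 (Protocol 9.2.1). I code the steps x = 0, 1, 2, 3 and read the fixed intercept as the log2 of the GMT.

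**The plan's own figure.** With a fixed intercept, SE = SD/√(n·Σx²), where Σx² = 14. On Day 15, 1.3/√(45·14) = 1.3/√630 = 0.052, as stated in Protocol 9.2.1, which confirms the coding. The same formula on Day 183 gives 1.1/√630 = 0.044, not the stated 0.040; that is a separate matter. If sampling error in the 1x10^11 vp GMT is counted, the Day 15 SE is (1.3/√45)·√(1/14 + 36/196) = 0.098.

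**What the slope averages.** Let y(x) be the mean log2 difference from the 1x10^11 vp group at step x. Then slope = [1·y(1) + 2·y(2) + 3·y(3)]/14. In terms of successive step changes d1, d2, d3 this is (6·d1 + 5·d2 + 3·d3)/14, or 43%, 36% and 21%. The slope equals d1 only if the later steps agree with it in this weighted sense.

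**Effect of curvature.** Assumption, not in the documents: mean log2 titer = floor + Emax·D/(D + ED50).

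| ED50 (vp) | Emax (log2) | y(1), y(2), y(3) | Slope | True first-step GMR | GMR from line | Slope / true |
|---|---|---|---|---|---|---|
| 1x10^11 | 2 | −0.504, −0.802, −0.929 | −0.350 | 0.71 | 0.78 | 0.69 |
| 1x10^11 | 4 | −1.008, −1.604, −1.857 | −0.699 | 0.50 | 0.62 | 0.69 |
| 2.5x10^10 | 2 | −0.462, −0.989, −1.342 | −0.462 | 0.73 | 0.73 | 1.00 |
| 1.1x10^10 | 2 | −0.302, −0.802, −1.298 | −0.414 | 0.81 | 0.75 | 1.37 |

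First row: (0.504 + 2·0.802 + 3·0.929)/14 = 4.89/14 = 0.35. Within this family the ratio in the last column does not depend on Emax.

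**Would a fit check reveal it?** None is specified. For illustration, a 5%-level lack-of-fit F test on 2 and 176 df has power of 13% in the first row and 39% in the second.

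**Precision of a direct contrast.** The SE of the difference between two group means on Day 15 is 1.3·√(2/45) = 0.274 log2. The 95% CI factor is 2^(1.96·0.274) = 1.45, up or down.

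**The case against.** The strongest reply is that the shape is already visible. Group GMTs with 95% CIs and several plots are committed, they assume no linearity, and any GMR is simply a quotient of two reported GMTs. The study is exploratory, plans no formal testing and names Emax models as an option. All of that stands. A reader might infer that the slope is the only dose-response output; it is only the sole model-based one. What remains missing is an interval for the contrast with 1x10^11 vp and a criterion for moving to another model.

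A reader might also infer that the slope almost ignores the step next to 1x10^11 vp. Weights proportional to x² are 0%, 7%, 29% and 64%, so 93% falls on the two lowest doses. Those are weights on each group's average loss per step from the reference, and the losses at steps 2 and 3 contain the first-step loss. As a successive step, the first carries 6/14 (43%), the largest share.

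Finally, the direct contrast is not always more accurate. For the first-step loss, combining bias with the SE of 0.098, the slope's root mean squared error is 0.18 log2 (ED50 1x10^11 vp, Emax 2), 0.32 (same ED50, Emax 4) and 0.15 (ED50 1.1x10^10 vp, Emax 2). Against 0.274 for the contrast, the slope is closer in two of the three. This is a reason to report both and not to let the GMR override the slope.

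**Conclusion.** The gap is real and modest. If the response is curved, the slope can misstate the first-step loss by roughly a third either way in the cases examined: about 69% of the true loss with ED50 1x10^11 vp, about 137% with ED50 1.1x10^10 vp, and essentially no bias near 2.5x10^10 vp. These sizes rest on an assumed Emax form. The power and precision figures also use the planning SD of 1.3 and 45 evaluable per group.

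Two stronger readings are tempting, but the documents do not support them. One is that the slope errs in the unsafe direction, understating loss where the release limit matters. No dose-response shape is given, the bias changes sign inside the tested dose range, and no release-limit value is stated; nor do the documents say that the slope or its lower limit would set that limit. The other is that the planned fit check would miss the curvature. No lack-of-fit test is planned, so its power illustrates what such a test could do, not a property of the plan.

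**What to change.** In SAP 5.3.1.1, also fit dose as a four-level factor in the Cohort 1 active groups. Report the GMRs of Groups 2, 3 and 4 versus Group 1 with 95% CIs at Days 15, 85 and 183, beside the slope. Statements about a given dose reduction can then be checked against an estimate that does not assume linearity. This stays descriptive and is compatible with the absence of formal testing.

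The cost is one more model per timepoint on data already being collected. Each GMR is less precise than the slope: SE 0.274 log2 on Day 15, with a 95% CI of about ×/÷1.45. The Emax fit can stay optional, since a curve with a floor has three parameters to estimate from four dose levels.

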### **5.3.1.2. Cellular Assays**

For IFN $\gamma$  enzyme-linked immunospot (ELISpot), N, median, quartiles and minimum and maximum of the actual values will be presented in tables and graphs. Subject profiles of the actual values over time will also be graphically presented.

Actual values will be shown as boxplots with the corresponding median and interquartile range per time point, including dots representing the individual subject values. In addition, boxplots over time will also be created with all the vaccine groups combined in one graph (without the individual subject dots). For the graphs, original values will be displayed on the log10 scale.

Reverse distribution curves of the actual values will be provided for selected time points.

#### For ICS and PBMC secreted cytokines (if available) analyses may include:

Total Cytokine response: the % of subsets expressing at least IFN $\gamma$ , TNF $\alpha$  or IL2 will be calculated for CD4 $^+$  and CD8 $^+$ . Tables with the corresponding descriptive statistics will be provided. Subject profiles of the actual values over time will be graphically presented.

Actual values will be shown as boxplots with the corresponding median and interquartile range per time point for each assay, including dots representing the individual subject values. In addition, boxplots over time will also be created with all the vaccine groups combined in one graph (without the individual subject dots). For the graphs, original values will be displayed on the log10 scale

For all cytokine combinations (IFN $\gamma$  and/or TNF $\alpha$  and/or IL2), bar charts reflecting the median magnitude of each combination of CD4 $^+$  and CD8 $^+$  T-cells will be graphically presented. Tables with the corresponding descriptive statistics will be provided.

Graphs may also be created to explore additional CD4 $^+$  and CD8 $^+$  cytokine responses included in the ICS panel (may include but not limited to IL4, IL17, CD17, CD45RA), based on data availability.

For the graphs, original values will be displayed on the log10 scale.

Scatterplots with humoral versus cellular assays may be provided for the most important time points.

The technical details for the calculation of the ICS values to be used in the graphs will be outlined in the DPS.

### **5.3.2. Immunogenicity Against Ad26**

For Ad26-specific VNA, the following statistics will be calculated and presented in tables: N, geometric mean§ and corresponding 95% CI of the actual values.

*§The mean and corresponding 95%CI will be calculated on the log10-transformed values, and then back-transformed.*

Subject profiles of the assays against the insert will be repeated, highlighting subjects with pre-existing immunity at baseline against the vector (Ad26-specific VNA).

Scatterplots of the Ad26-specific VNA at baseline versus the assays against the inserts will be provided for the most important time points. In these scatterplots the actual values will be shown, even if they are below the LLOQ.

## 6. SAFETY

Continuous variables will be summarized using the following statistics, as appropriate: number of observations (N), arithmetic mean (mean), 95% confidence interval (CI) for the mean, standard deviation (SD), standard error (SE), median, quartiles (Q1 and Q3), minimum and maximum. Frequencies and percentages (to one decimal place) will be generated for categorical variables.

Safety data will be summarized per cohort, vaccine group and study phase. In addition, for a selection of tables, data of Cohorts 2 and 3 may be pooled over cohorts.

Safety data will be presented only for the active period or phase, except SAEs which will be presented in all phases in which they were reported. The analysis phases are defined in Section 2.1.1. Denominator for the percentages is the number of subjects in the considered analysis set and period/phase for a certain vaccine group (incidence per 100 subjects/period).

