The planned primary and final analyses of all cohorts are detailed in Section 9.5. The primary analyses of Cohorts 2 and 3 will be combined.

After vaccination with study vaccine on Day 1, participants will remain under observation at the study site for a minimum of 30 minutes for presence of any acute reactions and solicited events, or longer if deemed necessary by the investigator. Any unsolicited and solicited local (injection site) or systemic AEs will be documented by the study-site personnel following this observation period. Participants will be given a thermometer, ruler, and a daily assessment (participant) diary with instructions for the proper recording of events. Each participant will record solicited local and systemic AEs and body temperature in the participant diary, beginning on the evening of the vaccination day and daily for 7 days after vaccination. Body temperature should be taken at approximately the same time each day. Study-site personnel will collect and review participant diary information and confirm the entries at the next visit.

The reporting periods of AEs, SAEs, and special reporting situations are detailed in Section 8.3. Reporting periods for concomitant therapy are outlined in Section 6.5.

Nasosorption samples using synthetic absorptive matrix (SAM) strips will be collected on Day 1 (prevaccination) and at 14 days and 3 and 6 months after vaccination (Section 8.1). Blood

samples to assess humoral and cellular immune responses will be collected on Day 1 (prevaccination) and at 14 days and 3 and 6 months after vaccination (Section 8.1). Clinical safety laboratory blood samples (Cohorts 2 and 3 only) will be collected at the screening visit, on Day 1 (prevaccination), and at 7 days after vaccination (or at the early exit visit if this visit is within 8 days after vaccination and the participant discontinues the study without withdrawing consent) (Section 8.2.3). Participant safety throughout the study will further be evaluated via physical examinations and vital signs (Sections 8.2.1 and 8.2.2, respectively).

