- Enrollment of new participants may continue based on the investigator's assessment of risks versus benefits, depending on the situation at a particular site, and the ability to monitor participant safety.
- Baseline visits for participants recently screened for this study should be postponed if the current situation does not allow for an orderly conduct of the study.

Site Visits

- When site visits are not possible due to local/national guidelines, sites should collect the assessments via telephone visits or home-based visits, if the participant allows. The actual visit date and the type of visit (ie, telephone or home-based visit) should be captured in the eCRF according to the eCRF completion guidelines. Procedures that cannot be performed during a home-based visit (eg, clinical assessments, blood samples, nasal samples and physical examination), should be excluded.

Vaccine Administration

- When planning for vaccination visits, local/national or institutional guidelines will be followed. The study vaccine must be administered by an (unblinded) pharmacist or other qualified individual at the study site. If this is not possible, a solution may be considered in consultation with the sponsor and taking into consideration participant safety.

Informed Consent Form

- Consenting and re-consenting of participants for the measures taken (including also remote consenting by phone or video consultation) will be performed as applicable and according to local guidance for informed consent applicable during the COVID-19 pandemic. The process is to be documented in the source documents.

Source Data Verification/Monitoring

- In case on-site monitoring visits are not be possible, the site monitor may contact the investigator to arrange monitoring visits and activities remotely (in accordance with site and local requirements). Additional on-site monitoring visits may be needed in the future to catch up on source data verification.

Site Audits

- During the COVID-19 pandemic and at the impacted sites, study site GCP audits with direct impact/engagement from the investigator and study site personnel would not be conducted in order to comply with national, local, and/or organizational social distancing restrictions. Additional quality assurance activities such as remote audits or focused review of study related documents may take place with limited impact/engagement if possible.

INVESTIGATOR AGREEMENT

COVID-19 Appendix
VAC18193 (JNJ-64400141/JNJ-64213175)

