**Table 1: Definitions of the Analysis Phases**

Phase	Phase	Period	Period	Interval	
				From	To
Screening	1			Date and time of signing the informed consent form	One minute prior to start of post dose period
Regimen	2	Post-dose	1	Date and time of first vaccination	
Minimum of:
 
 
a) 23:59 at the date of last contact (for early discontinuation from study)
 
b) 23:59 at the date of database cut-off date for interim analyses
 
c) Maximum (28 days after first vaccination at 23:59, scheduled visit 4 weeks after first vaccination at 23:59)
 

Follow-up	3			One minute after the end of the post-dose period	
Minimum of:
 
 
a) 23:59 at the date of last contact
 
b) 23:59 at the date of database cut-off date for interim analyses
 

Adverse events and concomitant medications will be allocated to the above phases and period, see details in Section 6.1 and Section 4.4 respectively. The regimen phase (post-dose period) is considered the active phase, the screening and follow-up phase are considered non-active phases.

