### 2.3.1. Full Analysis (FA) set

The FA set will include all participants who were randomized and received the study vaccine, regardless of the occurrence of protocol deviations. All safety and participant information analyses will be based on the FA set.

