## 3. INTERIM ANALYSIS AND DATA MONITORING COMMITTEE REVIEW

An internal Data Review Committee (DRC) will be commissioned for this study to discuss any safety issues and any situation meeting a specific study vaccination pausing rule (CTP Sections 9.6 and 7.3). Planned data reviews of the DRC are specified in CTP Section 4.1. The role and responsibilities of the internal DRC are detailed in the DRC Charter. The DRC analyses will follow the same statistical methods described in this SAP. A separate DPS document has been provided to describe specifications of individual tables, listings and figures to be generated in each DRC analysis.

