#### **6.2. Clinical Laboratory Tests (Cohorts 2 and 3 only)**

Laboratory toxicity grades will be determined according to the FDA toxicity grading table (CTP Section 10.2). If toxicity grades are not defined for a test, the abnormalities (above/below normal range) will be determined according to the clinical laboratory normal ranges.

Emerging abnormalities will be tabulated by worst toxicity grade. An abnormality (toxicity grade or abnormality based on normal ranges) will be considered as emerging in a particular period if it is worse than the baseline value. If the baseline is missing, the abnormality is always considered emerging. A shift from ‘abnormally low’ at baseline to ‘abnormally high’ post baseline (or vice versa) is also emerging. In case a laboratory test result is censored (no numeric value is available, but only a verbatim term) then a numeric value will be imputed by a value exceeding the cut-off value with one unit. (i.e., for “ $<x$ ”, subtract 1 unit from  $x$ . For “ $>x$ ” add 1 unit to  $x$ . E.g.,  $<3.45$  is imputed with 3.44).

In determining toxicity grades and abnormalities based on normal ranges, the following rules apply:

- Worst grades/abnormalities are determined over the whole observational period for each trial phase separately, including all post-baseline measurements of that phase.
- The abnormalities ‘abnormally low’ and ‘abnormally high’ are considered equally important, i.e. if a subject has both an abnormally low and an abnormally high value in a post-baseline phase, both abnormalities are shown in the tables. (This means that the sum of the percentages can be more than 100%)
- The grading scale of some parameters in the grading table has gaps (zones where no toxicity grade definition exists). Laboratory results falling in these zones will be allocated to the adjacent worst-case grade.
- If a laboratory value falls within the grading as specified in the grading table but also within the local lab normal limits, the value is considered as normal.
- For the grading on hemoglobin changes from baseline, the corresponding actual value should be at least grade 1. Toxicity grades of the actual values and changes from baseline will be tabulated separately.

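### Laboratory and vital-sign percentages are divided by all vaccinated participants in the phase, so a participant with no post-vaccination value looks the same as one with no emerging abnormality

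*SAP*

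**What the plan says.** SAP Section 6 fixes the denominator for safety percentages: "Denominator for the percentages is the number of subjects in the considered analysis set and period/phase for a certain vaccine group". SAP 2.3.1 names the set, "All safety and participant information analyses will be based on the FA set", and defines it without requiring any post-vaccination measurement: "The FA set will include all participants who were randomized and received the study vaccine, regardless of the occurrence of protocol deviations". In SAP Table 1 the post-dose period begins at "Date and time of first vaccination", so every member of the set is in the phase from the moment of injection.

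For laboratory tests SAP 6.2 says: "Emerging abnormalities will be tabulated by worst toxicity grade". It gives rules for a missing baseline, censored results, gaps in the grading scale and fasting status. It gives no denominator of its own, no category for participants not tested, and no rule for a missing post-vaccination result. SAP 6.3 counts participants with vital signs beyond the limits in its Table 3 and is silent on the same points.

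Under Protocol 4.1, safety blood samples in Cohorts 2 and 3 "will be collected at the screening visit, on Day 1 (prevaccination), and at 7 days after vaccination". That is one scheduled sample after vaccination, with an early exit visit within 8 days as the only scheduled substitute. The COVID-19 Appendix (Site Visits) allows telephone or home visits and adds: "Procedures that cannot be performed during a home-based visit (eg, clinical assessments, blood samples, nasal samples and physical examination), should be excluded". SAP Section 3 carries the method over to the committee reviews: "The DRC analyses will follow the same statistical methods described in this SAP".

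**The concern.** An all-vaccinated denominator suits adverse events, because a participant can report an event at any contact and SAP 6.1.4 states openly that no report means no event. A laboratory result exists only if blood is drawn. Applying the AE denominator to laboratory tables merges two kinds of participant: those tested with nothing emerging, and those not tested. The reader cannot separate them, because the SAP does not ask for the number tested.

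The SAP also leans in opposite directions. Where baseline is missing, 6.2 counts any abnormal value as emerging, which is cautious. Where the post-vaccination value is missing, the general denominator lowers the percentage, and the SAP does not comment on it.

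Scheduled laboratory safety tests exist only in the dose-up cohorts, where two dose levels are given for the first time (Protocol 4.2 and 4.3). Protocol 2.3.4 names transient neutrophil decreases and hemoglobin decreases as laboratory findings with this type of vaccine. With one scheduled post-vaccination sample, a single missed draw can remove all of a participant's post-baseline laboratory data.

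**Working it through.** **Inputs.** Groups 6 and 7 (Cohort 2) and Group 10 (Cohort 3) have 50 participants each, and the other groups in those cohorts have 25 (Protocol Table 2). Neither document gives a missing share m for laboratory samples, so m is left free and shown from 2% to 20% as an assumption.

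**The plan's own figures.** The documents state no figure for laboratory missingness. The nearest is Protocol Table 5, the one-sided 95% upper limit when no event is seen, 1 − 0.05^(1/n). For n = 25, 50 and 75 this gives 11.29%, 5.82% and 3.92%, matching the stated 11.3%, 5.8% and 3.9%. With 45 tested out of 50 the limit would be 6.44%. That shows the loss of information, but the SAP plans no confidence limits for laboratory percentages, so no planned output changes on this account.

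**Effect on the percentage.** Let N be the vaccinated participants in the group, n those with a post-baseline value, x those with an emerging abnormality, and m = (N − n)/N.

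- SAP percentage: x/N.
- Percentage among those tested: x/n.
- Hence x/N = (x/n) × (1 − m).

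Group of 50, x = 5, SAP percentage 5/50 = 10.0% throughout:

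| Without a value | Tested | Among those tested |
|---|---|---|
| 1 (2%) | 49 | 5/49 = 10.2% |
| 2 (4%) | 48 | 5/48 = 10.4% |
| 5 (10%) | 45 | 5/45 = 11.1% |
| 10 (20%) | 40 | 5/40 = 12.5% |

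Group of 25, x = 2, SAP percentage 2/25 = 8.0%: among those tested, 2/24 = 8.3%, 2/23 = 8.7% and 2/20 = 10.0% with 1, 2 and 5 missing.

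**Effect on a comparison.** Take two groups of 50, each with 20% abnormal among those tested. With nobody missing, 10/50 = 20.0% is reported. With 5 missing, 9/45 is reported as 9/50 = 18.0%. With 10 missing, 8/40 is reported as 8/50 = 16.0%. Unequal missingness alone produces an apparent difference of 2 to 4 percentage points.

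**What the new denominator cannot do.** Take 5 abnormal among 45 tested and 5 untested. The rate in all 50 lies between 5/50 = 10% (no untested participant abnormal) and 10/50 = 20% (all abnormal). The SAP percentage is always the lower end. The tested-only 11.1% is right for the whole group only if the untested resemble the tested. Showing the count without a value lets a reader form this range.

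**First DRC look.** A new-dose group has 20 × 2/5 = 8 participants in Cohort 2 and 16 × 2/4 = 8 in Cohort 3. One abnormal result is 1/8 = 12.5% under the SAP rule, and 1/7 = 14.3% of those tested if one sample is missing. In a blinded, pooled table of the 20 in Cohort 2, it is 1/20 = 5.0% against 1/19 = 5.3%.

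**Vital signs.** The Schedule of Activities has vital signs recorded after the 30-minute observation on Day 1 and again at later visits. A vaccinated participant with no post-vaccination vital sign should be rare, so the same rule has less effect in 6.3 than in 6.2.

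**The case against.** The strongest case against runs as follows.

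- *The SAP never says that untested means normal.* Correct. The only such rule is in SAP 6.1.4 and covers AEs. A reader might infer a deliberate coding rule for laboratory data, but there is none. The result follows from the denominator alone.
- *Table layouts are left to the data presentation specifications, which may show the number tested.* Possible; those specifications are not among the documents. But the SAP states a denominator and does not say that another document will replace it.
- *Few samples will be missing.* This has force. Day 8 in Cohorts 2 and 3 is an on-site visit; only Day 29 may be remote in the schedule. The COVID-19 Appendix also lets visits be delayed until on-site visits resume. A late or unscheduled sample still counts: the windows in SAP Table 2 apply to immunogenicity only, and 6.2 uses every post-baseline value in the phase, which lasts at least 28 days for participants still in follow-up (absent an earlier data cut-off).
- *The protocol's 10% exclusion figure gives the size.* It does not. It concerns Cohort 1 immunogenicity data and includes major protocol deviations.
- *Missingness will follow reactogenicity, and so dose.* A reader might infer this, because Protocol 2.3.4 reports more reactogenicity at higher Ad26 doses. No passage links reactions to missed samples. If the link existed, dividing by those tested would be biased too.
- *Enrollment decisions could be misled.* The documents do not support this. Pausing rule 5 (Protocol 7.3) uses counts of participants, clinically significant laboratory values are also captured as AEs (8.2.3), SAP 6 reports frequencies with percentages, and under Protocol 9.6 the DRC sees unblinded data only on request.
- *A stated denominator is a legitimate choice.* It is, for the share of vaccinated participants with a recorded abnormality. It is not the share of tested participants with an abnormality, and the tables should let the reader tell the two apart.

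**Conclusion.** The point holds as a matter of the SAP's own arithmetic. Section 6 states the denominator, 6.2 and 6.3 do not change it, and the percentage is multiplied by (1 − m) relative to the rate among those tested. The direction is always downward, and comparisons between groups shift when m differs.

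The size is modest: 0.2 percentage points in the group-of-50 example with one missing sample, and 1.1 points with five. It matters only if missingness is substantial or uneven, which the documents neither state nor rule out. Reading the tested-only rate as the rate for the whole group assumes that untested participants resemble tested ones. Analyses are descriptive and laboratory results are not a named endpoint. The point therefore concerns how accurately the safety tables read, and does not affect the validity of the pausing rules or the cohort sequence.

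**What to change.** In SAP 6.2 and 6.3, and in the DRC tables that follow the same methods, state that the denominator for each parameter is the number of FA-set participants in the group with at least one post-baseline value for that parameter in the phase. In each table, show by group the number with a value and the number without. The second part is essential, because the new denominator alone does not remove bias if missingness is related to reactogenicity. Keep the FA-set denominator for AE incidence.

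The cost is one sentence in each section and an extra line or two per table. Denominators will vary slightly between parameters and will differ from those in the AE tables, and some percentages will be slightly higher. No data collection changes.
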